#### 11.3 STOPPING RULES

We have set the following safety rules for PAPAGENO based on maternal and neonatal deaths that are possibly or definitely related to IMP. We have based these rules on the expected frequency of maternal and neonatal deaths in the population.

Maternal death rate in Malawi is 634 per 100,000 (UNICEF 2015). The combined stillbirth and neonatal death rate in Malawi is 44 per 1000 births (UNICEF 2015). With these expected death rates, we consider that a trebling of this rate would be grounds for serious concern. If such deaths were thought to be related or possibly related to study IMP, that will prompt a halt in recruitment pending review by the independent Data Monitoring and Safety Committee (iDMSC).

Our stopping rules will be based on the number of deaths expected within the first 25, 50 and 100 women recruited. The table below shows the number of expected deaths, and the number within each recruitment band that will trigger a rapid review by the iDMSC. The iDMSC will convene to review data within 14 working days. All the deaths are considered to be related, recruitment will be halted pending the iDMSC. If one or more of the deaths is considered unrelated, recruitment will continue pending review by the iDMSC. Whether or not the deaths are considered related, already recruited to the trial will continue on allocated IMP, pending the iDMSC review. The iDMSC will review unblinded data and advise whether the trial should be stopped, or the circumstances under which the trial should continue.

Number of women recruited	Expected number of maternal deaths	Number of maternal deaths that will trigger a halt to further recruitment.	Expected number of combined stillbirths and neonatal deaths	Number of combined stillbirths and neonatal deaths that will trigger a halt to further
Up to 25	Less than 1 (0.158)	1	1.1	recruitment. 3
Up to 50	Less than 1 (0.317)	1	2.2	6
Up to 100	Less than 1 (0.634)	2	4.4	13

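### Section 11.3 sets each perinatal death trigger at about three times the expected count for the top of its band but applies it to the whole band, so just past 25 and 50 women it asks for more than five times background, not the trebling the protocol names.

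*Protocol*

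**What the plan says.** Section 11.3 takes a background rate of 44 combined stillbirths and neonatal deaths per 1000 births, and 634 maternal deaths per 100,000. Its criterion is explicit: "we consider that a trebling of this rate would be grounds for serious concern". It explains the derivation: "Our stopping rules will be based on the number of deaths expected within the first 25, 50 and 100 women recruited". The table is said to show the expected deaths and "the number within each recruitment band that will trigger a rapid review by the iDMSC".

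The rows are indexed by number of women recruited:

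| Women recruited | Expected perinatal deaths | Perinatal trigger | Expected maternal deaths | Maternal trigger |
|---|---|---|---|---|
| Up to 25 | 1.1 | 3 | 0.158 | 1 |
| Up to 50 | 2.2 | 6 | 0.317 | 1 |
| Up to 100 | 4.4 | 13 | 0.634 | 2 |

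No rule is given for numbers between the band tops. Nothing says whether a lower row stays in force for its own women once recruitment has passed it.

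**The concern.** The expected count grows with every woman, but the trigger moves only at 25 and 50. One extra recruit takes the perinatal trigger from 3 to 6, and later from 6 to 13, while the expected count rises by 0.044. Just past each boundary the fixed count therefore stands for a much larger excess than the trebling the sponsor calls serious.

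This table is the only preset count of these deaths that obliges the committee to meet, within 14 working days. If it departs from its own criterion over long stretches of the trial, some true treblings that should prompt a review will not do so, or will do so later. The protocol itself fixes these numbers, so this is not a detail left to an analysis plan.

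**Working it through.** **Inputs (section 11.3).** Background perinatal rate 0.044; criterion 3 x 0.044 = 0.132; triggers 3, 6, 13. One birth per woman is assumed (known multiple pregnancies are excluded in section 4.3), and all deaths are counted, as in the table's expected counts.

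**Reproducing the table.** Three times expected at the band tops:
- 3 x 25 x 0.044 = 3.3, rounded down to 3
- 3 x 50 x 0.044 = 6.6, rounded down to 6
- 3 x 100 x 0.044 = 13.2, rounded down to 13

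The triggers are band-top values.

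**Multiple of background needed at n women** = trigger / (0.044 n). The last column is 0.132 n rounded down, minimum 3.

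| n | Trigger in table | Expected | Multiple | Scaled trigger |
|---|---|---|---|---|
| 25 | 3 | 1.100 | 2.7 | 3 |
| 26 | 6 | 1.144 | 5.2 | 3 |
| 50 | 6 | 2.200 | 2.7 | 6 |
| 51 | 13 | 2.244 | 5.8 | 6 |
| 60 | 13 | 2.640 | 4.9 | 7 |
| 75 | 13 | 3.300 | 3.9 | 9 |
| 90 | 13 | 3.960 | 3.3 | 11 |
| 99 | 13 | 4.356 | 2.98 | 13 |

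**Effect on detection.** Outcomes are taken one at a time, each a death with probability 0.132 (trebled) or 0.044 (background). A trial counts as triggered once the cumulative count first reaches the boundary in force at that n. The running rule is max(3, 0.132 n rounded down).

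| Triggered by | Trebled, table | Trebled, running | Background, table | Background, running |
|---|---|---|---|---|
| n = 25 | 66% | 66% | 10% | 10% |
| n = 51 | 77% | 85% | 10% | 16% |
| n = 75 | 77% | 89% | 10% | 16% |
| n = 100 | 82% | 90% | 10% | 16% |

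The rules are identical up to 25 women. Most of the gap is already there by 51, so much of it comes from the step at 26. After the step at 51 the table adds almost nothing until well past 75.

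**What n counts.** The sequence above treats each outcome as known at once, which describes completed pregnancies, not recruits. Women enter at 12 to 28 weeks. Assuming uniform entry over that range, delivery at about 39 weeks and steady recruitment over 12 months, only about 14 women have delivered when the 51st is recruited. If n is women recruited, a trebling is then detected in roughly 57% of trials under either rule. A running rule indexed by completed pregnancies gives about 90%.

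**Maternal row.** Three times expected is 0.476, 0.951 and 1.902, rounded up to 1, 1 and 2. On that rounding a running rule first requires 2 deaths when 3 x 0.00634 x n exceeds 1, at n = 53 (1.008). It would differ from the table only for women 51 and 52.

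**The case against.** The strongest reply is that the multiples at single values of n exaggerate the harm. A reader might infer that the rule goes nearly blind at the 51st woman: at a trebled rate the chance of 13 or more deaths among 51 is 1.3%, against 68% for 6 or more. That comparison ignores the triggers of 3 and 6 that have already been running. In sequence, the table has fired by n = 51 in 77% of trebled trials, and the median first trigger is at n = 20 under both rules. This part of the reply stands, and the cumulative figures are the ones to use.

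Second, section 11.3 speaks of deaths within the first 25, 50 and 100 women, which permits a cohort reading: six deaths among the first 50 would still trigger a review whenever they occur. The text neither states nor excludes this. On that reading the later women's outcomes still count only towards 13, so the step remains for them and the ambiguity itself needs settling.

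Third, the committee has other information. Section 9.1 gives it interim unblinded data, section 12 requires serious events to be reported within 24-48 hours, and section 12.1 makes neonatal deaths reportable regardless of relationship. It would therefore be wrong to infer that a trebling passes unseen. What is weakened is the preset obligation to review.

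Fourth, a reader might extend the criticism to the maternal row, where 2 deaths at 51 women is 6.2 times the expected 0.323. The documents do not support this as a banding fault. The coarseness comes mainly from whole-number triggers: 1 death at 25 women is already 6.3 times expected at the top of its band.

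**Conclusion.** The point holds for the perinatal triggers. The table contradicts the protocol's own trebling criterion over most of the second and third bands, by up to 5.2 and 5.8 times background just past the boundaries, and it does not say whether earlier rows persist.

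The practical loss is moderate: about 8 percentage points of overall detection (82% against 90%), bought back at about 6 points more false reviews. These figures assume outcomes known in sequence, independent births, all deaths counted, and a trebling across both arms together. They do not show that a trebling usually escapes review, and they do not carry over to the maternal row. Under the assumed entry and delivery times, finer steps indexed by women recruited would change little, so the unit of n matters at least as much as the step.

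**What to change.** Reconcile the table in section 11.3, and the committee charter, with the sponsor's stated criterion. One way that keeps the protocol's own rate, multiple and rounding is to tabulate the perinatal review trigger for every 10 completed pregnancies (women with a known birth outcome, not women recruited) as 3 x 0.044 x n rounded down, minimum 3:

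| Completed pregnancies | 10 | 20 | 30 | 40 | 50 | 60 | 70 | 80 | 90 | 100 |
|---|---|---|---|---|---|---|---|---|---|---|
| 3 x 0.044 x n | 1.32 | 2.64 | 3.96 | 5.28 | 6.60 | 7.92 | 9.24 | 10.56 | 11.88 | 13.20 |
| Trigger | 3 | 3 | 3 | 5 | 6 | 7 | 9 | 10 | 11 | 13 |

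State that deaths are counted cumulatively over all completed pregnancies, which also settles the status of the first-50 row. The maternal row needs no change on this account.

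The cost is a longer table and more reviews. With outcomes in sequence, the chance of at least one false review at background rates rises from about 10% to 16% under the running rule; steps of 10 leave small residual jumps and come slightly below that. Under section 11.3 such a review does not by itself halt recruitment unless all the deaths are considered related.

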# 12.1 **DEFINITIONS**

An **adverse event** (AE) is any untoward medical occurrence in a clinical trial participant which does not necessarily have a causal relationship with an investigational medicinal product (IMP).

An **adverse reaction** (AR) is any untoward and unintended response to an IMP which is related to any dose administered to that participant.

A serious adverse event (SAE), serious adverse reaction (SAR). Any AE or AR that at any dose:

• results in death of the clinical trial participant – including neonatal deaths\*\*

- is life threatening\*;
- adverse medicine experience
- requires in-patient hospitalisation^ or prolongation of existing hospitalisation;
- results in persistent or significant disability or incapacity\*\*
- congenital anomaly/birth defect or spontaneous abortion (miscarriage)
- cancer new onset or recurrent \*\*
- Immune Dysfunction: new diagnosis either of HIV or life-threatening immunodeficiency diseases.
- An important medical event, based on appropriate medical judgment that jeopardises the participant and may require intervention to prevent one of the outcomes listed above.

\*Life-threatening in the definition of an SAE or SAR refers to an event where the participant was at risk of death at the time of the event. It does not refer to an event which hypothetically might have caused death if it were more severe.

\*\* Reportable events regardless of the relationship to the IMP.

^Any hospitalisation that was planned prior to enrolment (such as hospitalisation for delivery of the baby) will not meet SAE criteria. Any hospitalisation that is planned post enrolment will meet the SAE criteria.

A suspected unexpected serious adverse reaction (SUSAR) is any AR that is classified as serious and is suspected to be related to the IMP contained in the Reference Safety Information (RSI) for that IMP. The RSI is contained in the Summary of Product Characteristics (SPC) for the IMP, which was submitted to the PMPB as part of the approvals process. The RSI is usually comprised of the 'undesirable effects' detailed in section 4.8 of the SPC; this section is used to assess the expectedness of an SAR.

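### Section 11.3 gives incompatible rules for pausing recruitment after deaths; read literally, one earlier unrelated death keeps recruitment open even when related deaths alone reach the trigger count

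*Protocol*

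**What the plan says.** Protocol section 11.3 makes four statements about what deaths do to recruitment.

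1. **Opening.** The rules are "based on maternal and neonatal deaths that are possibly or definitely related to IMP". After quoting national death rates the section adds: "we consider that a trebling of this rate would be grounds for serious concern". It continues: "If such deaths were thought to be related or possibly related to study IMP, that will prompt a halt in recruitment pending review".
2. **Lead-in to the table.** The tabulated counts trigger a rapid review by the independent committee, which convenes within 14 working days.
3. **Operative sentences.** If all the deaths are considered related, recruitment is halted pending the committee (the sentence seems to have lost its opening conditional). Then: "If one or more of the deaths is considered unrelated , recruitment will continue pending review by the iDMSC".
4. **Table headers.** The maternal column is headed "Number of maternal deaths that will trigger a halt to further recruitment", and the stillbirth and neonatal column is headed in the same way.

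The counts for up to 25 / 50 / 100 women are 1 / 1 / 2 maternal deaths and 3 / 6 / 13 stillbirths plus neonatal deaths. Women already recruited stay on allocated treatment under either outcome, so the rule governs new entrants only.

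**The concern.** A recruitment pause has to be carried out the same way by each site, the sponsor and the committee. Here the same events lead to different actions depending on which sentence is followed. If only related deaths are counted, as in the opening, the sentence about unrelated deaths has no role. If all deaths are counted, as the all-cause expected numbers suggest, that sentence overrides the table headers.

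The relatedness wording also shifts: possibly or definitely, then related or possibly related, then simply related. Section 12.5.2 uses four categories, including probably related.

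At stake is whether new women are enrolled during the review period after the count of related deaths has been reached. The trial expects background stillbirths and neonatal deaths, so a rule that one unrelated death can block is exposed to ordinary mortality.

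**Working it through.** **Inputs (Protocol 11.1 and 11.3).** Stillbirth plus neonatal death rate p = 44/1000 = 0.044. Maternal death rate 634/100,000 = 0.00634. Level of concern: three times the background rate. Recruitment 8-9 women per month. Entry at 12 to 28 weeks (4.2). One birth per woman is assumed.

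**Reproducing the table.** Expected deaths = n × rate.
- Stillbirth/neonatal: 1.1 / 2.2 / 4.4. Trebled: 3.3 / 6.6 / 13.2, rounded down to 3 / 6 / 13.
- Maternal: 0.158 / 0.317 / 0.634. Trebled: 0.476 / 0.951 / 1.902, rounded up to 1 / 1 / 2.

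The table agrees with its stated basis.

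**The statements on one case.** Among the first 25 women, one unrelated neonatal death is followed by three related ones.

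| Statement | Action |
|---|---|
| Opening | Halt |
| Table header | Halt |
| Lead-in | Review; silent on halt |
| Operative sentences | Recruitment continues |

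**Chance of at least one background stillbirth or neonatal death**, 1 − (1 − p)^n:

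| Completed births | 25 | 50 | 100 |
|---|---|---|---|
| All background deaths judged unrelated | 67.5% | 89.5% | 98.9% |
| Half judged unrelated (p = 0.022) | 42.7% | 67.1% | 89.2% |

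These are upper limits, because few women have delivered while recruitment is open. Assume constant recruitment of 100 over 52.2 weeks (1.917 per week), entry uniform over 12-28 weeks and delivery at 40 weeks. The lag to delivery is then uniform on 12-28 weeks. Births by week T are 1.917 × (T − 12)²/32 for T between 12 and 28, and 1.917 × (8 + T − 28) after that.
- 25th woman, T = 13.04: 0.07 births, 1 − 0.956^0.07 = 0.3%
- 50th woman, T = 26.09: 11.9 births, 41%
- 100th woman, T = 52.18: 61.7 births, 94%

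**Reading where only the deaths making up the count matter.** At a trebling, two thirds of deaths are excess. The chance that all of the first c deaths are attributable is (2/3)^c: (2/3)³ = 29.6%, (2/3)⁶ = 8.8%, (2/3)¹³ = 0.5%.

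**Share of halts that survive the operative sentences**, given that related deaths alone reach the count, with excess rate 2p judged related and background p judged unrelated, over completed births:
- No unrelated death at any time in the band: 0.1325/0.3796 = 35%, 0.0328/0.2752 = 12%, 0.00143/0.1001 = 1.4%.
- No unrelated death before the count is reached: (2/3)^c × P(total ≥ c) / P(related ≥ c) = 0.2963 × 0.6591/0.3796 = 51%, 0.0878 × 0.6615/0.2752 = 21%, 0.00514 × 0.5680/0.1001 = 2.9%.

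**Maternal column.** The chance of at least one background death is 14.7% / 27.2% / 47.1%. On the first of the two calculations above, about 86% / 73% / 53% of halts survive.

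**The case against.** The best defence is a two-step reading: the number of deaths triggers review, and relatedness then decides whether recruitment pauses meanwhile. Section 11.3 handles lactic acidosis in that way. On this reading, setting all-cause counts against all-cause expected numbers is coherent and is not an error. It also explains why the lead-in speaks of review. It does not explain the table headers, nor why one unrelated death should keep recruitment open when related deaths alone meet the count.

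Several limits on the size stand:
- Order matters. If the first deaths up to the count are all related, recruitment is already halted, and nothing says a later unrelated death lifts the halt.
- Not every background death will be judged unrelated. Section 12.4 assesses all events as though the woman takes metformin, and 12.5.2 lets timing make an event possibly related.
- The completed-birth percentages overstate the exposure during recruitment, and once 100 women are in there is no recruitment left to halt.

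A reader might infer that the halt is almost disabled, or that participants lose their main protection. The documents do not support that. Most maternal halts survive at 25 and 50 women and about half at 100, and unblinded review within 14 working days takes place either way. Taking 14 working days as about 20 calendar days, some 5-6 women would enrol meanwhile (8 × 12/365.25 × 20 = 5.3; 9 × 12/365.25 × 20 = 5.9). Section 17 allows termination at any time, and 15.3 provides for urgent safety measures.

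A reader might also infer that stillbirths escape causality assessment. That is not established: 12.1 does not name them, but 12.2 does not exempt them, and they may be reported as important medical events.

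**Conclusion.** Section 11.3 contradicts itself and cannot be executed as written. The contradiction rests on the text alone and needs no assumption.

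Its practical size depends on the column and the recruitment band. For stillbirths and neonatal deaths it is modest at 25 women, where hardly any births will have occurred, and substantial towards 100. There the chance of an earlier background death is about 94% under constant recruitment and delivery at 40 weeks, if every background death is judged unrelated. The narrower reading does not rescue the rule: at the trebling it was built to detect, the full set of 6 or 13 deaths would seldom all be attributable. The maternal column is less affected.

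The consequence is continued enrolment until the committee meets, not loss of oversight. The stillbirth reporting gap is secondary: 11.3 counts stillbirths and needs a causality judgement on them, yet its opening sentence and the serious adverse event list in 12.1 leave them unnamed.

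**What to change.** The sponsor should reconcile the opening sentences, the lead-in, the operative sentences and the table headers of section 11.3 into one rule that states:

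- whether the counts are of all deaths or only of related deaths;
- which of the 12.5.2 causality categories qualify;
- whether reaching a count triggers review, a halt or both;
- what effect an unrelated death has when related deaths alone reach the count, including one that occurs after a halt has begun.

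Which of the present statements should prevail is for the sponsor and the independent committee to decide. The thresholds need not be reopened for this point.

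As a secondary change, state in 12.1 that stillbirths follow the serious adverse event reporting and causality route, so that the combined count in 11.3 can be applied when it is needed.

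The cost is one reworded paragraph with matching table headers, and one line in 12.1. The downside is possibly a temporary recruitment pause and a few more expedited reports.

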### 7.4 CESSATION OF STUDY MEDICATION

Medication (but not study participation) will be stopped in any of the following circumstances:

- Fetal demise in utero
- Diagnosis of diabetes (gestational or otherwise)
- If the participant develops severe pre-eclampsia or HELLP syndrome
- Delivery of the baby (end of pregnancy)
- If the clinical team judge that immediate delivery is advised in the next 48 hours, for example in the case of development of severe sepsis or evidence of fetal compromise.

Metformin should be stopped temporarily if any of the following occur:

- Elective surgery (metformin should be stopped 48 hours prior)
- Severe diarrhoea or vomiting or fever
- Reduced fluid intake
- Non steroidal anti-inflammatory drug therapy for more than two days

Metformin can be restarted once the event/ episode above has ceased:

Participants who stop treatment following administration of the first dose of intervention or any doses thereafter will not be replaced by additional recruited participants. Where possible, data will continue to be collected from all participants after initial enrolment to allow intention to treat analysis.

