# 8.6 PRECAUTIONS

**Overdose:** Hypoglycaemia has not been seen with metformin hydrochloride doses of up to 85g, although lactic acidosis has occurred in such circumstances. High overdose PAPAGENO: Protocol Version 1.0 07/03/2019

of metformin hydrochloride or concomitant risks may, very rarely, lead to lactic acidosis. Lactic acidosis is a very rare complication of metformin, occurring in less than 4 per 100,000 patients. Lactic acidosis is a medical emergency and must be treated in hospital. The most effective method to remove lactate and metformin hydrochloride is haemodialysis.

**Dehydration**: In case of dehydration (severe diarrhoea or vomiting, fever or reduced fluid intake), metformin should be temporarily halted and contact with a health care professional is recommended. Treatment may re-commence on advice of the local Principal investigator

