The most serious adverse effect of metformin is lactic acidosis, with an estimated frequency of 4 per 100,000. In a sample size of 100, we would expect 0.0004 cases of lactic acidosis. Any events of lactic acidosis will prompt a review by the iDMSC within 14 working days. If lactic acidosis is considered related to the study medication, recruitment will halt temporarily, pending review by the iDMSC. If lactic acidosis is not considered related, recruitment will continue, pending review by the iDMSC. Those already recruited to the trial will continue on allocated IMP pending iDMSC review. The iDMSC will review unblinded data and advise whether the trial should be stopped, or the circumstances under which the trial should continue.

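### Section 11.3 keeps recruited women on study drug after a lactic acidosis without excepting the woman affected, and no section makes the event itself a mandatory stop

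*Protocol*

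**What the plan says.** Protocol section 11.3 calls lactic acidosis the most serious adverse effect of metformin and gives it its own rule. "Any events of lactic acidosis will prompt a review by the iDMSC within 14 working days". If the event is judged related, recruitment halts for the time being; if not, recruitment goes on. Both branches end with the same sentence on study drug: "Those already recruited to the trial will continue on allocated IMP pending iDMSC review". A near-identical sentence closes the rule on deaths: "already recruited to the trial will continue on allocated IMP, pending the iDMSC review".

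Section 7.4 has two lists. The first is introduced by "Medication (but not study participation) will be stopped in any of the following circumstances" and has no restart clause. It covers fetal death, diabetes, severe pre-eclampsia or HELLP, delivery, and a judgement that delivery is needed within 48 hours. The second covers temporary stops (planned surgery, severe diarrhoea, vomiting or fever, low fluid intake, NSAIDs beyond two days) and ends "Metformin can be restarted once the event/ episode above has ceased". Neither list names lactic or metabolic acidosis.

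Section 8.6 says: "Lactic acidosis is a medical emergency and must be treated in hospital". It names haemodialysis as the best way to clear lactate and metformin, but gives no instruction about study drug. Section 7.2, under emergency unblinding, has a general rule: in an emergency where the attending clinician thinks continued metformin may be harmful, study treatment should stop.

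**The concern.** A site with a case of lactic acidosis will look for an instruction about that woman's tablets. The only sentence tied to the event says that recruited women stay on them, and the section headed for stopping medication does not mention the event. The right action has to be inferred from a conditional clause in the unblinding section, to which 11.3 does not refer.

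Two comparisons make the gap look unintended. Acute metabolic acidosis, with lactic acidosis as an example, keeps a woman out of the trial (4.3), but nothing carries that contraindication forward to a woman already on treatment. And section 8.9 has an explicit stop and restart rule for iodinated contrast, because contrast can lead to lactic acidosis, while the acidosis itself has neither.

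What is at stake is the safety of one participant if the event occurs. No estimate or analysis depends on it.

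**Working it through.** **The sections that could stop her drug, taken in turn**

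1. *11.3, lactic acidosis rule.* Drug continues in those recruited, with no exception for the affected woman.
2. *11.3, rule on deaths.* Nearly the same sentence, but harmless there. A woman who has died takes no drug, and after a stillbirth or neonatal death 7.4 has already stopped it, through "Fetal demise in utero" or through delivery. In the lactic acidosis rule the woman may be alive, pregnant and holding a supply.
3. *7.4, first list.* This gives a lasting stop in some acidosis cases: if the fetus dies, or if immediate delivery is advised, for instance for severe sepsis or fetal compromise. It does not reach a woman who recovers with the pregnancy continuing.
4. *7.4, second list, and 8.6 on dehydration.* Vomiting, fever or poor intake would interrupt the drug. The permission to restart belongs to those episodes, not to acidosis.
5. *8.8.* Study treatment stops at once on a major fall in urine output. The trigger is urine output, and restart is not mentioned.
6. *7.2.* Stops the drug if the attending clinician considers metformin potentially harmful. It has no restart clause.
7. *7.3 and 8.4.* The investigator may withdraw her or change the regimen. These permit a stop and do not require one.
8. *4.3.* Acidosis is an exclusion at entry only.

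So several routes can stop her drug. None is triggered by lactic acidosis as such, and none addresses restart after it.

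**How likely the event is**

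Inputs: 100 women randomised 1:1, so 50 on metformin; 4 per 100,000 (11.3); 3.3 to 4.3 per 100,000 patient-years (8.8); about 30 weeks of treatment (trial summary). A short exposure of 12 weeks is my assumption (entry at 28 weeks, delivery at 40).

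The plan's own figure first: "In a sample size of 100, we would expect 0.0004 cases of lactic acidosis". From its inputs, 100 × 4/100,000 = 0.004, so the printed value is ten times too small. Counting only the metformin arm, 50 × 4/100,000 = 0.002.

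Chance of at least one case = 1 − exp(−expected cases):

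| Assumption | Expected cases | Chance of any case |
|---|---|---|
| 3.3 per 100,000 patient-years, 12 weeks: 50 × 12/52 = 11.54 patient-years | 0.00038 | 0.04% |
| 4.3 per 100,000 patient-years, 30 weeks: 50 × 30/52 = 28.85 patient-years | 0.00124 | 0.12% |
| 4 per 100,000 women | 0.002 | 0.20% |

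Section 8.8 says that some NRTIs may raise the risk but gives no multiplier, so none is applied.

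**The window before review**

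Fourteen working days are 18 to 20 calendar days, without public holidays. At 2000 mg (4 tablets) a day that is 72 to 80 tablets. A monthly visit can supply up to 5 weeks, or 5 × 7 × 4 = 140 tablets. This is a ceiling that assumes uninterrupted full dosing through a hospital emergency. It is not an expected exposure.

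**The case against.** The strongest reply is that 11.3 is a rule about the trial, not about one patient. It contrasts halting with continuing recruitment, and the sentence on those already recruited is the natural counterpart. The matching sentence for deaths cannot refer to a woman who has died. The patient herself is handled elsewhere: a clinician told in 8.6 that this is a hospital emergency, and how to remove metformin from the blood, will judge more of it harmful, and 7.2 then says to stop. Sections 7.3 and 8.4 give further freedom to act. The event is very rare, and the SPC, which is separate and not shown, may cover stopping during treatment.

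Most of this stands, and it rules out several stronger readings that a reader might take from the text:

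- *The protocol requires the affected woman to stay on drug, or gives no means of stopping it.* It does not: 7.2 with 8.6 points to stopping, and 7.3 and 8.4 allow it.
- *Every other stop that an acidosis might trip is temporary.* The first list in 7.4 has no restart clause and can apply through fetal death or advised delivery.
- *The protocol permits a restart before the committee meets.* It is silent on restart after lactic acidosis. Silence is not permission, but it is not a bar either.

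What the reply does not remove is that the event-specific sentence is broader than its evident purpose, and that stopping depends on one clinician's judgement under a clause to which 11.3 does not point. That judgement is least certain where the event is thought unrelated, for example put down to an NRTI.

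**Conclusion.** The point holds as a minor safety drafting error. The sentence in 11.3 does not except the affected woman, no section makes lactic acidosis itself a mandatory or permanent stop, and no section bars a restart after recovery. The chance that the gap is ever tested is about 0.04% to 0.2%, given the protocol's rates, 50 women on metformin and the assumed 12 weeks at the low end. Harm would also need clinicians to continue or restart the drug despite 7.2 and 8.6, which is unlikely. It merits a correction because the event is the one the protocol ranks as most serious and the remedy is a few words.

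Two related slips are clerical. The count of 0.0004 should be 0.004, and no rule depends on it, since any single case prompts review. Sections 7.2 and 8.3 send the reader to a paragraph 5.9 that does not exist; 7.4 is evidently meant.

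**What to change.** - In 11.3, make the subject of the lactic acidosis sentence *Other women already recruited*, and add at its end: *the affected woman stops study drug permanently*.
- In 7.4, add *suspected or confirmed lactic or metabolic acidosis* to the first list, which has no restart clause.
- Clerical: replace the reference to paragraph 5.9 with 7.4 in sections 7.2 and 8.3, and 0.0004 with 0.004 in 11.3.
- Optional: a line in 7.4 on other metformin contraindications from 4.3 that arise during treatment, such as shock or cardiac failure. The 11.3 sentence does not concern them, and the SPC may already cover them.

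The cost is an amendment to the wording and, rarely, one extra discontinuation. Such a woman stays in follow-up, because 7.4 stops medication and not participation.
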